2.3 Drugs or Biologics: N/A

2.4 Medical Devices. N/A

2.5 Behavioral Intervention: Both the active and control conditions are behavioral interventions. See description above.

PARTICIPANT MANAGEMENT

7.0 Inclusion and Exclusion Criteria*

3.1 Eligibility Criteria:

Inclusion Criteria

- 1) Must be a parent aged 18+ (primary caregiver) of 2-6-year-old child with PFD
- 2) Child must be receiving outpatient PFD treatment at CMH
- 3) The parent must have a clinically significant elevation on at least one measure of parent MH (using established clinical cutoffs). Parents will be included regardless of whether the child has a new diagnosis or established diagnoses

Exclusion Criteria

- 1) Parent has significant cognitive impairments
- 2) Parent does not speak English
- Parent unable to obtain high speed internet at home

3.2 Equitable Selection: We are excluding non-English speaking participants because we are providing a behavioral intervention and do not have a translated version of the intervention available. In the future, we hope to translate this

intervention for non-English speaking patients but are unable to do this for the present study.

3.3 Vulnerable Populations: *Check any vulnerable populations that are being targeted for enrollment into the study: (Members of the following populations may not be included as participants in the research unless selected here.)*

 Children/Minors (under 7 years of age)	 CM Employees
 Children/Minors (7-17 years of age)	 CM Students/Residents/ Fellows
 Neonates (infants less than 30 days old)	 Economically or Educationally Disadvantaged Persons
 Neonates of Uncertain Viability (infants less than 30 days old)	 Prisoners
 Non-Viable Neonates (infants less than 30 days old)	
 Wards of the State	
 Fetuses	
 Pregnant Women	
 Adults with impaired decision-making capacity	

- Children with pediatric feeding disorder will be enrolled, and adequate provisions will be made to solicit the informed consent of parents and/or guardians. Informed consent of children in this study would not be appropriate because children enrolled are under the age of 6 years and many of these children have developmental delays. Parents will be given sufficient time to decide if the study is right for them and will be given all the options during the consent conversation. Participants will be informed that they can withdraw from the research at any time.

8.0 Local Number of Participants

4.1

	Total consented (before meeting inclusion criteria)	Group 1 (Active treatment)	Group 2 (Control)	Total (meet criteria and randomized)
Enrollment Goal: Number of participants to be enrolled = the number of participants to be consented or to be screened for chart reviews.	80	20	10	30

Approximately 60% of subjects consented will not meet inclusion criteria after taking quantitative measures and so 80 subjects will need to be enrolled to meet 30 randomized subjects. If number of randomized subjects reaches 30 prior to 80 being enrolled, enrollment will cease.

SHORT TITLE:

9.0 Identification and Recruitment of Potential Participants*

4.2 Identification of Potential Participants:

How will participants be identified? (Check all that apply)

Chart reviews

By their treating physician who will then provide the study team's contact information to the potential participant/family

By their treating physician who will obtain patient/family permission to share contact information with the study team

Self-refer in response to IRB approved advertisements or websites

Through Cerner or other CM sources (e.g. databases, billing records, pathology reports, admission logs, etc.) May involve access of records by individuals not involved in the patient's care.

List of candidates provided through the Data Report Request Form

Registry of individuals interested in research opportunities

Past participant list

Participants will roll-over from another research study: Study #

Other:

4.3 Pre-Screening prior to HIPAA Authorization

Will any of the identification methods checked above involve access to Protected Health Information (PHI) prior to obtaining HIPAA Authorization?

Yes

No

- *If yes, a "Partial Waiver of HIPAA Authorization" is required. Be sure to make this selection in the "HIPAA & Confidentiality" section below and complete [Addendum E: Waiver/Alteration of HIPAA Authorization](#)*

SHORT TITLE:

4.4 Recruitment of Potential Participants:

Parents will be screened at outpatient clinic visits to the CMH feeding clinic. Parents who agree to participate will then complete parent MH measures via REDCap on a tablet during the clinic visit. No PHI will be collected at this time. Potential subjects that meet inclusion criteria after completing the screening tool will be asked to participate in the study. At that time a ICF will be given to them and reviewed. All questions will be answered and adequate time will be given for a decision.

•

10.0 Procedures

[figure not shown]
Parents who meet inclusion criteria and sign consent will be randomized to either PACT-F or an attention control (control) condition using block randomization, such that an equal number of patients presenting for a new diagnosis and with an established diagnosis are randomized to each group. Participants will be blind to treatment condition (single blind study). See Figure 1 below for procedures. Intervention. Parents randomized to PACT-F will complete two 90-minute PACT-F sessions individually with a study interventionist, 2-weeks apart (see Table 2 for intervention content). Parents randomized to the control group will complete two 90-minute sessions individually with a study interventionist, 2-weeks apart (focused on nutrition education). The control intervention will be parallel to the PACT-F intervention in all ways, including interactive components and the face-to-face time with health professionals (interventionists). The control condition intervention has already been developed by [name] research team and covers a range of nutrition and healthy lifestyle topics including USDA's *MyPlate*. Interventionists for both conditions will be individuals with at least master's degree training in mental health or a related field. The interventions will take place remotely via telehealth. The team has expertise in remote delivery of therapy in both clinical and research environments. Both arms of the intervention will be manualized and interventionists in both arms will be trained using didactics and role playing with the PI. Intervention fidelity will be monitored by audio recording all sessions. The PI ([name]) will review video recordings each week and conduct weekly supervision.

Due to the nature of the study, the participants will be blinded to the group assignment during treatment. This is necessary as knowledge of whether they are in the treatment or control group may change behaviors of the participants. We will therefore not be able to give specific descriptions of the treatments in each group in the Informed consent form. Participants will be informed of their group assignment after they have completed the 3-month follow up and if they were in the control group be given the opportunity to participate in the treatment group. There is no difference in risk for either group.

Once the 3-month follow up is complete the subjects will be contacted and unblinded and control subjects will be offered the active treatment.

SHORT TITLE:

Figure 1

5.2 Blood and Other Specimen Collection:

N/A

11.0 Surveys and Psychometric Testing:

- Parent Mental Health (MH) Measures.
 - PHQ-9. A 9-item self-report measure of depressive symptoms. Scores of 10 or more indicate probable depression.
 - GAD-7. A 7-item self-report measure of anxious symptoms. Scores of 10 or more indicate probable anxiety.⁸⁷

SHORT TITLE:

- IES-R. A 22-item self-report measure of posttraumatic stress symptoms. Scores of 33 or more indicate clinically significant posttraumatic stress.
- PSS. A 10-item self-report measure of perceived stress. Scores of 14 or more indicate clinically significant stress.
- AAQ-2. A 7-item self-report measure of psychological flexibility and experiential avoidance, which are targets of the behavioral treatment.
- Child Health.
 - PedsQL 4.0 (Generic). A 23-item parent-proxy measure of child quality of life, with versions specific to child age (2-4 years, 5-7 years) that each result in standardized total scores and domain-specific scores of physical functioning, emotional functioning, social functioning, and school functioning.
 - BPFAS. A 35-item parent-proxy report of child mealtime and feeding behavior.
- Observational Behavioral Coding. Parents will record a representative family mealtime over Teams at baseline, post-intervention, and at 3-month follow-up. A research assistant will facilitate the recordings over Teams using procedures routinely employed in [name] prior RCTs. The recordings will be coded using the Dyadic Interaction Nomenclature for Eating (DINE) coding scheme. The DINE is a well-established measure of mealtime behavior that has been studied in a variety of populations and has good psychometric properties.⁷⁴ The DINE measures parent-child interactions by coding three subscales: parent behaviors, child behaviors, and child eating behaviors. DINE coding will be completed by research assistants trained by the PI. The research assistants will be blinded to the intervention condition. Each video will be double-coded, and discrepancies will be resolved by meetings between the two coders and consultation with the PI.
- Exit survey: Parents will complete an exit survey at the 3 month visit via RedCap on their feelings about the study and offer a chance to give feedback on their experiences.

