4.0 Study Endpoints

Parents will complete the standard study battery at baseline, post-intervention, and 3-month follow-up.

Quantitative Measures. Feasibility success is defined as recruitment rate above 60%, and retention, assessment completion, and intervention completion rate above 80%.

SHORT TITLE: PACT Study

Demographics. Parents will provide information on their own and child's age, sex/gender, race/ethnicity, education, and socioeconomic status.

- Parent Mental Health (MH) Measures.
 - PHQ-9. A 9-item self-report measure of depressive symptoms. Scores of 10 or more indicate probable depression.
 - GAD-7. A 7-item self-report measure of anxious symptoms. Scores of 10 or more indicate probable anxiety.⁸⁷
 - IES-R. A 22-item self-report measure of posttraumatic stress symptoms. Scores of 33 or more indicate clinically significant posttraumatic stress.
 - PSS. A 10-item self-report measure of perceived stress. Scores of 14 or more indicate clinically significant stress.
 - AAQ-2. A 7-item self-report measure of psychological flexibility and experiential avoidance, which are targets of the behavioral treatment.
- Child Health.
 - PedsQL 4.0 (Generic). A 23-item parent-proxy measure of child quality of life, with versions specific to child age (2-4 years, 5-7 years) that each result in standardized total scores and domain-specific scores of physical functioning, emotional functioning, social functioning, and school functioning.
 - BPFAS. A 35-item parent-proxy report of child mealtime and feeding behavior.
- Qualitative Measures. Qualitative surveys will be completed by parents at the 3-month follow-up, focused on factors that impact feasibility. Feasibility of 1) recruitment procedures, 2) intervention procedures, and 3) measure completion.

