28.0 Statistical Analysis*

10.1 Data will be analyzed using SPSS. We will conduct descriptive statistics to evaluate the research endpoints of this study. We will

SHORT TITLE:

conduct correlations between demographic factors and endpoints to evaluate relationships that may influence these endpoints.

10.2 Quantitative Feasibility Analyses. Descriptive statistics (frequency counts, %s) will determine recruitment, retention, assessment, and intervention delivery success and will be compared to identified benchmarks of success (recruitment rate above 60%, and retention, assessment completion, and intervention completion rate above 80%). Factors that may impact success will be evaluated in relation to these outcomes using t- and chi-squared tests.

10.3 Qualitative Feasibility Analyses. Parent free text responses to feasibility questions will be imported into NVivo 12 software for coding. A coding tree will be developed a priori and periodically revised to include relevant inductive codes as emergent themes arise. Qualitative responses will then be double coded by PI and a graduate research assistant. Interrater reliability will be coded, with the goal of achieving 80% interrater reliability. PI mentor will provide direct supervision for data collection and analysis.

10.4 Proof of concept analyses. We use the Reliable Change Index (RCI; success defined as $RCI > 1.96$) to determine if there is a reliable signal of change for participants who are in the PACT (active treatment) group from baseline to post-treatment and follow-up. The RCI is a psychometric criterion used to evaluate whether change is significant at the level of the individual. An RCI will be calculated for each participant in the PACT (active treatment) group, using the following formula: $RCI = \text{observed difference score between measurements} / \text{standard error of measurement of the difference}$. We will assess proof of concept for change in parent stress, parent anxiety, and parent behavior at meals (measured by the DINE).

10.5 Given the feasibility and proof-of-concept nature of this study, we are interested in seeing if these study procedures are feasible and if there are meaningful improvements (e.g., several points of improvement on rating scales) rather than statistical significance. The sample size was therefore selected to ensure that a large enough group of participants can be evaluated to be reflective of a heterogeneous group of parents.

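### Diagnosis status (new versus established) constrains the randomization, but neither the RCI analysis nor the list of factors related to endpoints includes it

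*Combined protocol and SAP*

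**What the plan says.** Section 7.0 admits both kinds of family: "Parents will be included regardless of whether the child has a new diagnosis or established diagnoses". Section 10.0 then makes diagnosis status a constraint on block randomization, "such that an equal number of patients presenting for a new diagnosis and with an established diagnosis are randomized to each group". These are the only two places where the document mentions the factor.

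The analysis section (28.0) has three parts that bear on it:

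- **Item 10.1** plans correlations between demographic factors and endpoints, to look for influences on those endpoints. Section 4.0 lists the demographics as parent and child age, "sex/gender, race/ethnicity, education, and socioeconomic status". Diagnosis status is not in the list.
- **Item 10.4** calculates an RCI for each parent in the active arm, from baseline to post-treatment and follow-up: "We will assess proof of concept for change in parent stress, parent anxiety, and parent behavior at meals (measured by the DINE"). It gives no split or adjustment by diagnosis status, and no rule for summarising the individual results across parents.
- **Items 10.2 and 10.6** relate feasibility outcomes to factors that may affect them. Item 10.2 names t- and chi-squared tests. Item 10.6 refers to baseline characteristics for recruitment, assessment and intervention delivery, and hypothesis 2.2 does so for retention. Neither place itemises the term.

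**The concern.** Balancing a factor between arms protects a comparison of arms. The proof-of-concept analysis makes no such comparison, because it uses the active arm alone. The balance built into the randomization therefore does nothing for that result, and any relation between diagnosis status and change passes straight into it.

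Such a relation is plausible on the document's own account, though the document gives no figure for it. Section 7.0 requires every child to be in outpatient feeding treatment. Section 3.0 says treatment works largely through what parents do at home, including structured meals and positive interaction at mealtimes. Positive mealtime behavior is also a study outcome, scored with the DINE. Families presenting for a new diagnosis may be taking up that advice during the trial, so usual care could move the outcome differently in the two groups.

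At stake is how the pilot is read. One figure for all PACT parents could reflect change in both groups or in only one, and the later efficacy study would not know which. Item 10.5 justifies the sample as reflecting a heterogeneous group of parents, yet improvement is not described by the one source of heterogeneity that the randomization controls.

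**Working it through.** **Step 1. The plan's own sample-size figure.** Section 8.0 states that "Approximately 60% of subjects consented will not meet inclusion criteria after taking quantitative measures", and that "80 subjects will need to be enrolled to meet 30 randomized subjects". Forward: 80 × (1 − 0.60) = 32, close to 30. Backward: 30 / 0.40 = 75. The stated pair implies 1 − 30/80 = 62.5% screen failure, which fits the word approximately. The point does not rest on this figure. The plan states no alpha, power or effect size to reproduce.

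**Step 2. How many parents per stratum.** Section 8.0 plans 20 active and 10 control. An even split gives 20/2 = 10 PACT and 10/2 = 5 control parents per stratum. This is an assumption, for two reasons:

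- If section 10.0 means that each diagnosis type goes in equal numbers to both arms, the arms would be 15 and 15, against 20 and 10 in section 8.0.
- If it means equal numbers of new and established families within each arm (10/10 and 5/5), recruitment would need quotas, and none are stated.

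**Step 3. How case mix moves a single active-arm figure.** Let k of the 20 PACT families be new. Pooled share = (k × p_new + (20 − k) × p_est) / 20. Both sets of shares are assumed.

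| New / established | 60% v 20% | 25% v 5% |
|---|---|---|
| 5 / 15 | (3 + 3)/20 = 30% | – |
| 6 / 14 | – | (1.5 + 0.7)/20 = 11% |
| 10 / 10 | (6 + 2)/20 = 40% | (2.5 + 0.5)/20 = 15% |
| 14 / 6 | – | (3.5 + 0.3)/20 = 19% |
| 15 / 5 | (9 + 1)/20 = 50% | – |

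If section 10.0 fixes the mix at 10/10, the figure no longer varies with recruitment, but it still does not show where the change occurred.

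**Step 4. How much a split can show.** Exact (Clopper-Pearson) 95% intervals at an assumed 50% response are 27% to 73% for 10 of 20, and 19% to 81% for 5 of 10. Power of a two-sided 5% Fisher test with 10 v 10, by enumeration:

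| Assumed shares | Power |
|---|---|
| 25% v 5% | 5% |
| 60% v 40% | 5% |
| 70% v 30% | 24% |
| 80% v 20% | 64% |

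Two further binomial results, also 10 v 10:

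- With true shares of 25% and 5%, the new group exceeds the established group by at most one responder (or not at all) with probability 38%.
- With 15% in both groups, a gap of two or more responders in either direction still appears with probability 33%.

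**The case against.** The strongest reply has four parts.

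1. **Feasibility may already be covered.** Diagnosis status must be known before randomization, so it is naturally a baseline characteristic, and items 10.2 and 10.6 analyse those. This stands. A reader might infer that no planned analysis uses the factor at all. The document does not support that: for feasibility the term is open, and the gap is one of naming. For improvement there is no such opening.
2. **Nothing shows that the two groups change differently.** This stands as to size. A reader might also picture established families as stable, so that only new families have a reason to change. The document says only that the diagnosis is established. Those children are also in treatment, and at entry, whichever the diagnosis status, "The parent must have a clinically significant elevation on at least one measure of parent MH". Selection on a high score can produce regression toward the mean in both groups.
3. **Subgroups of 10 are noisy.** This stands. In the milder case of step 3, case mix moves the pooled count only from 2.2 to 3.8 of 20, while the exact 95% interval for 3 of 20 runs from 3% to 38%. Step 4 shows that a split can miss a real difference or suggest a false one. This argues against tests and subgroup claims, but not against a table.
4. **Splitting the active arm cannot separate a PACT effect from change on entering care.** This stands. A higher share among new PACT families could equally mean that PACT works better for them. The table therefore has to include the control arm. Covariate adjustment is not the answer either, since the plan contains no model or contrast between arms to adjust.

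**Conclusion.** The point holds for the improvement analyses. The one factor named as constraining the randomization is missing from the active-arm RCI in item 10.4 and from the demographic factors in item 10.1. For feasibility, it is only unclear whether the factor is included.

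The size cannot be taken from the document. Under assumed shares of 60% and 20%, the active-arm figure ranges from 30% to 50% as the mix runs from 5 to 15 new families of 20. Under 25% and 5%, it ranges from 11% to 19% as the mix runs from 6 to 14. These are illustrations, and they also assume that individual RCI results will be summarised as a count, which item 10.4 does not say. Pooling is inferred from the absence of any split.

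The omission does not invalidate the pilot, and a split would not establish a subgroup effect. It is an inexpensive gap in description that is best closed before the data are seen.

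**What to change.** - **Item 10.1:** add new versus established diagnosis to the factors examined in relation to endpoints.
- **Items 10.2 and 10.6:** name it explicitly among the baseline characteristics examined for recruitment, retention, assessment and session completion.
- **Item 10.4:** calculate the RCI in the control arm as well, and report RCI counts by diagnosis status in both arms, with denominators and without subgroup tests.
- **Sections 8.0 and 10.0:** reconcile the equal-number wording with the 20/10 allocation, and say whether equality is meant between arms or within each arm. If it is meant within arms, state how recruitment will achieve it.

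**Cost:** a few table columns and some sentences. Diagnosis status is already needed to randomize, and section 4.0 has parents complete the same battery at all three time points, so no extra visits or participants are needed.

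**Downside:** with about 10 PACT and 5 control parents per stratum if the split is even, the table can only describe. It cannot by itself separate a PACT effect from change under usual feeding care, and the report should say so beside the table.

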12.0 Follow-up

13.0 Genetic Analysis Information

5.1 N/A

14.0 Sharing of Results with Participants

5.2 A study summary of individual results will be offered to all subjects when they complete the study.

SHORT TITLE:

15.0 Risks to Participants*

5.3 This study is minimal risk, and the only foreseeable risk is the loss of confidentiality in the event of a data breach. Precautions have been taken to ensure data confidentiality, such as data storage in a secure REDCap database, with only trained/approved study staff having access to the data.

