26.0 Data Collection*

8.1 We will collect questionnaire data from parents enrolled in the study. We will have parents video record a mealtimes with them and their child through a facilitated Microsoft Teams call. PHI accessed in the medical record will include patient Name, MRN, DOB, and Visit Date, phone number, address, and email address.

8.2 The PHI from the medical records will be abstracted by chart review. Questionnaires will be collected via REDCap survey. Mealtimes will recorded via a facilitated Microsoft Teams call. All data will be securely stored as outlined in the Data Management plan below.

8.3 Sensitive Data: We are not collecting sensitive data.

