27.0 Adverse Events and Unanticipated Problems*

9.1 Monitoring: Participating parents will be able to reach study staff at any time if they experience distress and will have ongoing contact with the RUBI team during their regular course of care. We will monitor parent responses to the depression screening measure (PHQ-9) as the responses are submitted. If a parent endorses clinically significant depression or endorses a positive response on the item asking about suicidal ideation, the PI (a licensed psychologist) will contact the parent to conduct a safety assessment and provide the parent with appropriate referrals for intervention as indicated (e.g., emergency room).

9.2 Reporting: We will follow Policy 5.11 Reportable Events of the CM Research Program Policies and Procedures in regard to reporting adverse events and other unanticipated problems to the CM IRB.

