32.0 Setting & Locations*

14.1 All visits will take place either during a MDC feeding clinic visit at Adelle Hall in the Gastroenterology outpatient clinics or via tele-video conferencing using Microsoft Teams with the participant at home. Measures completion will be done via redcap system.

14.2 As this study is focused on the mental health of caregivers, psychological resources will be readily available for caregivers if necessary. As there are no physical procedures being done a need for medical resources are not expected.

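### Section 15.0 names data breach as the only foreseeable risk, but sections 27.0 and 32.0 plan for parent distress and PHQ-9 safety triggers; the passages need reconciling

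*Combined protocol and SAP*

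**What the plan says.** Section 15.0 (5.3) rates the study as minimal risk and states that "the only foreseeable risk is the loss of confidentiality in the event of a data breach". The precautions it lists concern data storage and access.

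Section 27.0 (9.1) goes further. It says that "Participating parents will be able to reach study staff at any time if they experience distress", and that PHQ-9 answers are monitored on submission. It then sets a trigger: "If a parent endorses clinically significant depression or endorses a positive response on the item asking about suicidal ideation". When the trigger is met, the PI is to contact the parent, assess safety and "provide the parent with appropriate referrals for intervention as indicated (e.g., emergency room"). Section 32.0 (14.2) adds that "psychological resources will be readily available for caregivers if necessary".

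The population is chosen for symptoms. Section 7.0 (3.1) requires: "The parent must have a clinically significant elevation on at least one measure of parent MH (using established clinical cutoffs"). For the PHQ-9, section 4.0 gives the cutoff: "Scores of 10 or more indicate probable depression".

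Four other places bear on the point:

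- Section 17.0 (17.1) says that the IRB decides on risk from the answers in the two sections before it, which are 15.0 and 16.0.
- Section 10.0 states that risk does not differ between the arms.
- Section 26.0 (8.3) reads "Sensitive Data: We are not collecting sensitive data".
- Section 27.0 (9.2) refers event reporting to institutional Policy 5.11, which the document does not reproduce.

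**The concern.** A protocol that writes a response plan for an event has foreseen that event. Section 15.0 cannot then say that a confidentiality breach is the only thing foreseen. The omission falls in a section that the IRB is told to rely on, while the text that contradicts it (27.0) is not one of those two sections.

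Two things are at stake. The first is disclosure. The risk section is the natural source for the risk wording in the consent form and the screening information sheet. If they copy it, parents with clinical elevations would not be told that questionnaires, sessions or a recorded meal might distress them, or that certain PHQ-9 answers can bring a call from the PI. The second is the safety record. Section 28.0 plans no summary of safety triggers or distress contacts, so the statement in 10.0 that risk is equal in both arms would never be set against data.

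**Working it through.** There is no stated figure to reproduce. The check is a comparison of text, followed by a small illustration.

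**1. The passages side by side**

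| Section | Content | Consistent with breach as the sole foreseeable risk? |
|---|---|---|
| 15.0 (5.3) | Confidentiality breach only | This is the statement under test |
| 27.0 (9.1) | Staff reachable at any time for a distressed parent | No: distress is provided for |
| 27.0 (9.1) | PHQ-9 trigger, PI safety assessment, referral | Not clearly: may detect illness already present |
| 32.0 (14.2) | Psychological support on hand, because the study concerns caregiver mental health | No, although worded conditionally |
| 7.0 (3.1) | Entry requires a clinical elevation | Makes activation of 27.0 more likely |

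The distress clause is the clearest conflict. Section 3.0 supports it: it describes each meal as a potential stressor for these parents, and section 4.0 then has a meal recorded at baseline, post-intervention and 3 months.

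**2. Is activation foreseeable from the plan's own criteria?** Section 27.0 does not define clinically significant depression. If it means the PHQ-9 cutoff of 10 in section 4.0, every parent who qualifies for the study on the PHQ-9 meets the trigger at entry. Parents who qualify only on another measure (GAD-7, IES-R or PSS) need not.

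**3. How many parents are selected for symptoms?** Section 8.0 expects about 60% of 80 not to meet criteria: 80 × (1 − 0.60) = 32 eligible, for 30 randomised. This counts parents above any cutoff. It does not count parents who will be distressed or meet the trigger, and the documents give no figure for that.

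**4. Illustration with an assumed trigger rate.** Let q be the chance that a parent meets the trigger, with parents independent. Then P(at least one) = 1 − (1 − q)^n.

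| Assumed q | n = 30: expected count | n = 30: P(at least one) | n = 80: expected count | n = 80: P(at least one) |
|---|---|---|---|---|
| 2% | 0.6 | 0.45 | 1.6 | 0.80 |
| 5% | 1.5 | 0.79 | 4.0 | 0.98 |
| 10% | 3.0 | 0.96 | 8.0 | 0.9998 |
| 20% | 6.0 | 0.999 | 16.0 | about 1.00 |

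From 5% upward, use of the procedure is more likely than not even among the 30 randomised. At 2% it is close to even.

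**5. Does the n = 80 column apply?** Only if screening answers are monitored, and the text leaves this open. Section 27.0 speaks of participating parents. Section 9.0 (4.4) says that no PHI is collected at screening, and Addendum E says that the questionnaire database is de-identified. A PI contact needs an identifiable parent, so these passages must also be reconciled.

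**The case against.** The strongest reply is that section 15.0 lists risks caused by the study, while section 27.0 is a conditional safety net for illness that parents bring with them. A high PHQ-9 at entry may reflect baseline symptoms. Section 16.0 says that the approach has reduced parent distress in other pediatric populations. Protection is already planned, through real-time monitoring and assessment by a licensed psychologist. On this view the conflict is only one of wording.

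Much of that stands, and it rules out four stronger readings that a reader might infer:

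- **That parents are not told.** The consent pages were removed before review and the screening information sheet is not in the text. The only content that section 10.0 says is withheld from the consent form is the specific description of the treatments.
- **That such events would count as unanticipated.** Classification depends on Policy 5.11, which is not reproduced. Nothing in the document says that the list in 15.0 decides it.
- **That the study expects to cause depression or suicidal ideation.** Section 27.0 says what happens if these are endorsed. No section says that study procedures worsen symptoms.
- **That the minimal-risk category is wrong.** Mild, managed distress can sit within minimal risk, and nothing here shows otherwise.

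The reply does not rescue the sole-risk claim. The distress clause is not limited to illness present at entry, and section 15.0 does not say that it is limited to study-caused risk. The equal-risk statement in 10.0 may be true, since both arms share the battery, recordings and contact time; it is simply untested. The sensitive-data statement is weaker ground, because the term is undefined. It is a supporting point only.

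**Conclusion.** The contradiction is real and should be corrected. Section 15.0 excludes every foreseeable risk except a data breach, while 27.0 and 32.0 plan for distress in parents admitted because of clinical elevations.

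The size is modest. The point concerns all 30 randomised parents and, if screening answers are monitored, up to 80 screened. It changes no endpoint, sample size or analysis. The consequence for disclosure holds only if the consent form and information sheet follow 15.0. The probabilities above rest on assumed trigger rates and on independence, and the conclusion does not depend on them.

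**What to change.** 1. **Section 15.0:** reconcile it with 27.0 and 32.0. Drop the claim of a sole risk and list emotional distress from questionnaires, sessions or mealtime recording as a foreseeable minimal risk.
2. **Screening information sheet and consent form:** check both against the revised 15.0. State that PHQ-9 answers are monitored and may lead to contact by the PI. This requires the sponsor to settle whether screening answers are covered, and to reconcile 27.0 with 9.0 (4.4) and Addendum E.
3. **Section 26.0 (8.3):** define sensitive data or correct the statement, given the suicidal ideation item, the posttraumatic stress measure and the family video.
4. **Section 28.0:** add a descriptive table of PHQ-9 safety triggers and distress contacts by arm, with baseline separated from post-randomisation so that symptoms present at entry are not read as effects of the study. Use this alongside the statement in 10.0 that risk does not differ. With 20 and 10 parents the table describes; it does not test.

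The cost is a wording amendment, revised participant documents and one table from data already collected or easily logged. The one drawback is that some parents may answer the PHQ-9 less openly once they know it is monitored.
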